Aspiration is the most significant etiology of airway complications and anesthesia death.¹³ To prevent pulmonary aspiration during anesthesia, it is important to determine the level of inspiratory pressure minimizing gastric insufflation during pulmonary ventilation. A randomized trial has showed that inspiratory pressure of 15 cmH₂O can decrease the occurrence of gastric insufflation during induction of anesthesia for non-paralyzed non-obese patients.¹⁴ Although morbid obesity predisposes to the development of pulmonary aspiration during anesthesia¹³, there is still little evidence regarding the safe inspiratory pressure to prevent the occurrence of gastric insufflation during positive ventilation.

Poor glottis visualization during tracheal intubation

Obese patients present a unique challenge to airway management for anesthesia providers. Obesity-related obstructive sleep apnea and reduced neck movement contribute to a higher risk of difficulty intubation.¹⁵ Previous study has showed that video laryngoscopy provides better glottis visualization and reduces the time to successful intubation with similar intubation success rates compared to Macintosh direct laryngoscopy in morbidly obese patients.^{4,16} However, video or direct laryngoscopy may be inappropriate for patients with limited mouth opening, loose teeth or dental prosthesis. It remains unclear for the utility of other video intubating devices used in obese population.

Video intubating stylet is a useful tool for the placement of tracheal tubes. For tracheal intubation, a tracheal tube is preloaded over the video stylet, which is passed through the oral cavity to visualize the epiglottis and guided to glottic opening via a monitor.¹⁷ Video intubating stylet has been reported to be more effective and safer than Macintosh laryngoscope in the placement of double-lumen tubes in thoracic surgery.¹⁸⁻²⁰ Video intubating stylet has also been demonstrated useful in tracheal intubation for cervical spine-immobilized patients.^{21,22} Nevertheless, previous work in obese patients was limited.

Hemodynamic instability in bariatric surgery

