PONV is a common adverse event among patients following bariatric procedures with a reported rate of 18% to 82%.³⁰⁻³² PONV may increase the risk of wound dehiscence and prolong the length of stay in the post-anesthesia recovery room.³³ Besides, PONV represents one of the frequent reasons for unanticipated re-hospitalization after bariatric surgery.³⁴ In particular, morbidly obese people have a greater risk of PONV compared to those with body mass index < 35 kg·m⁻² after bariatric surgery.³⁵

Current practice guidelines recommend the use of single or multiple types of antiemetics as PONV prophylaxis according to Apfel risk prediction score.³⁶ However, these guidelines are primarily based on evidence derived from general population.^{7,23} There are few studies investigating the clinical strategy to mitigate PONV risk pertinent to obese patients. In addition, it remains unclear whether intravenous dexamethasone, a common prophylactic agent for PONV, is associated with potential adverse effects in obese people, such as hyperglycemic response, wound infection and delayed healing.^{7,23,37} Since obese patients are susceptible to the injury of hyperglycemia and associated wound infection^{38,39}, it is of great importance to elucidate the risk and benefits of dexamethasone in the prevention of PONV.

Research Objective

The main objective of this study is to investigate the optimal anesthesia for obese patients undergoing bariatric surgery in the strategies of positive pulmonary ventilation, tracheal intubation technique, hemodynamic monitoring, and PONV prophylaxis, as the followed:

1. To evaluate the effectiveness and adverse effect of intravenous dexamethasone for PONV prophylaxis
2. To determine the safe inspiratory pressure to prevent the occurrence of gastric insufflation during facemask ventilation using point-of-care ultrasonography of antrum
3. To compare the effectiveness and safety between video intubating stylet and video laryngoscope in the placement of tracheal tubes
4. To apply minimally invasive CO monitors in guiding goal-directed hemodynamic therapy and assess its impact on major complications and postoperative recovery

Novelty and Implication

1. Considering the growing prevalence of obesity and its potential impact on perioperative care, the optimal anesthesia strategy for obese patients should be further explored.

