2. Investigation of perioperative use of dexamethasone will enrich the current literature of PONV prophylaxis for obese patients.
3. The study will determine the airway pressure threshold to prompt gastric insufflation during positive ventilation, providing a practical guidance in the airway management of anesthesia and cardiopulmonary resuscitation.
4. This study will evaluate the application of video intubating stylet in the tracheal intubation of obese patients, offering another evidence-based intubation technique.
5. This research will also provide valuable evidence regarding the treatment effect of intraoperative GDHT in obese patients, which may offer an important implication for precision hemodynamic management in the obese people.
6. The study will provide important evidence for an Enhanced Recovery After Surgery (ERAS) protocol of bariatric surgery.

Materials and Methods

We will conduct a factorial parallel randomized controlled trial using permuted block randomization and stratified randomization and conforming to the CONSORT Statement to investigate multiple clinical outcomes in obese patients undergoing laparoscopic sleeve gastrectomy (LSG) at Shuang Ho Hospital, Taipei Medical University, New Taipei City, Taiwan.⁴⁰⁻⁴² Four randomizations will be conducted, including intravenous dexamethasone for PONV, various inspiratory pressure of mask ventilation, three tracheal intubation techniques, and goal-directed hemodynamic therapy using minimally invasive cardiac output monitoring. (Figure 2) A computer-generated list of randomizations will be applied for these group allocations. Each patient will be randomly assigned a specific study number and group in four randomizations, and these assignments will be then enclosed in envelopes and sealed.

Inclusion criteria are patients aged ≥ 20 years with body mass index $\geq 30 \text{ kg}\cdot\text{m}^{-2}$ undergoing LSG at Shuang Ho Hospital. Exclusion criteria are as the following:

1. Pregnant or lactating women
2. Severe cardiopulmonary distress, including left ventricular ejection fraction $< 40\%$, double or triple vessel disease, New York Heart Association functional classification ≥ 3 , peripheral oxygen saturation by pulse oximetry (SpO_2) $< 90\%$ in room air, and moderate to severe pulmonary hypertension.
3. Previous esophageal, gastric, or duodenal surgery.
4. Previous head and neck surgery or radiation therapy
5. Previous cervical spine injury

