According to prior study⁶⁴, at least 80 patients in each group of GDHT and control are needed to detect a significant difference, accepting a type I error of 5% and type II error of 10% with anticipated incidence of postoperative major complications 30% in GDHT group and 55% in control group in Substudy 4.⁶⁵ To allocate 60 subjects to each group of video intubating stylet, video laryngoscopy, and direct laryngoscopy in Substudy 3, a total of 180 subjects are needed for the factorial trial. There are about 120 obese people undergoing LSG at our hospital per year. Considering the patient selection criteria and possible patient refusal, an estimated sample of 90 patients will be recruited per year in this trial. Therefore, it will take about 2 years for patient recruitment.

Statistical Analysis

Baseline patient characteristics and outcome variables will be compared between two groups using chi-square tests or Fisher's exact tests for categorical variables and either t tests or Wilcoxon rank sum tests for continuous variables, as appropriate. For three and four group comparisons, chi-square tests or Fisher's exact tests will be used for categorical variables and either one-way ANOVA or Kruskal-Wallis rank test for continuous variables, as appropriate. *Post hoc* pairwise comparisons will be performed using the Bonferroni correction. For longitudinal data, generalized linear mixed models or generalized estimating equations models will be used to analyze the association between exposure variables and outcomes of interest. For time to event data, Kaplan-Meier method and log-rank test will be applied for group comparisons. Multivariable logistic regression, simple linear regression, or Cox proportional hazards regression analyses will be used to identify potential influential factors of outcomes. A two-sided significance level of 0.05 will be used to define statistically significant difference. All the statistical analyses will be conducted using Statistics Analysis System (SAS), Version 9.4 (SAS Institute Inc., Cary, NC, USA).

References

1. World Health Organization. Fact sheets: Obesity and overweight. <https://www.who.int/en/news-room/fact-sheets/detail/obesity-and-overweight> (accessed on December 5, 2020).
2. Blüher M. Obesity: global epidemiology and pathogenesis. *Nat Rev Endocrinol.* 2019;15:288-98.

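### Substudy 2 promises a safe or threshold inspiratory pressure, but its planned tests ignore the order of the four pressures and estimate no threshold

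*Combined protocol and SAP*

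**What the plan says.** The aim is a pressure. Background states the gap: "there is still little evidence regarding the safe inspiratory pressure to prevent the occurrence of gastric insufflation during positive ventilation". Research Objective, item 2, is "To determine the safe inspiratory pressure to prevent the occurrence of gastric insufflation during facemask ventilation", with antral ultrasonography named as the tool. Novelty and Implication, item 3, promises that "The study will determine the airway pressure threshold to prompt gastric insufflation during positive ventilation". The Substudy 2 title also speaks of a threshold.

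Substudy 2 randomises to 10, 15, 20 or 25 cmH₂O. Its primary outcome is an episode of gastric insufflation. Two diagnoses are then defined, one by ultrasound and one by auscultation, made by assessors blinded to each other. The outcome sentence does not say which one counts.

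The Statistical Analysis section handles a four-group categorical outcome with "For three and four group comparisons, chi-square tests" or Fisher's exact test, after which post hoc "pairwise comparisons will be performed using the Bonferroni correction". Logistic regression appears only in a general sentence: the models "will be used to identify potential influential factors of outcomes". The level is fixed for the whole plan: "A two-sided significance level of 0.05 will be used to define statistically significant difference".

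Sample Size Estimation says that "a total of 180 subjects are needed for the factorial trial". It gives no insufflation rate, power or precision for Substudy 2.

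**The concern.** The question is at what pressure the risk of insufflation becomes too high. The planned overall test asks whether the four risks are all equal, and it treats the pressures as unordered labels. The pairwise tests ask whether two given pressures differ. Neither yields a pressure, and the plan does not state:

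- a risk level against which a pressure would be judged;
- an interval for each arm's risk;
- a pressure-response estimate.

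Followed exactly, the analysis ends with p values. Any threshold would have to be chosen after the data are seen. The only pre-specified way of separating one pressure from another is the set of corrected pairs. If these have little power, a non-significant pair is an easy but unsound basis for calling the higher pressure safe. The plan offers the result as guidance for airway management and resuscitation, so it should follow from a stated rule.

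**Working it through.** **The plan's own figure.** There is none for Substudy 2. The only powered figure is 80 per group for Substudy 4 (30% vs 55%, two-sided 5%, 90% power):

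n = [1.96·√(2·0.425·0.575) + 1.2816·√(0.30·0.70 + 0.55·0.45)]² / 0.25² = (1.370 + 0.867)² / 0.0625 ≈ 80.1, so 81 after rounding up.

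That agrees with 80 for practical purposes, but it has no bearing on Substudy 2.

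**Inputs for Substudy 2.** The total is 180 (Sample Size Estimation). No allocation ratio is given for the pressure arms; equal allocation is assumed, so 180/4 = 45 per arm. Four arms make six pairs, so the Bonferroni level is 0.05/6 = 0.0083 (critical z = 2.638). All insufflation risks below are assumptions.

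**Pairwise power.** The normal approximation is

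power ≈ Φ{[d − 2.638·√(2·p̄(1−p̄)/45)] / √[(p₁(1−p₁) + p₂(1−p₂))/45]}.

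For 10% vs 20%: Φ[(0.10 − 2.638·0.0753)/0.0745] = Φ(−1.32) ≈ 9%.

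Exact enumeration of the pooled z test over 10-point steps gives about 13% for 5% vs 15%, falling to about 5% for 30% vs 40%. Even the widest pair, 10 vs 25 cmH₂O, has only 52, 66 and 78% power under the three gradual rises in the table.

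**Overall test.** The chi-square statistic is X² = Σ 45(pᵢ − p̄)² / [p̄(1−p̄)], on 3 df. Shuffling the pressures among the arms leaves it unchanged, which is the sense in which it ignores order. It was compared by simulation (100,000 trials per shape, 45 per arm) with two order-respecting tests:

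- *Isotonic*: the same statistic with each pᵢ replaced by its order-restricted fit. It is run in both directions at one-sided 0.025 each (critical value 5.89; chi-bar-square weights 1/4, 11/24, 1/4, 1/24). Its two-sided type I error is between 4 and 5% at equal risks of 5 to 30%.
- *Trend*: two-sided Cochran-Armitage with equally spaced scores.

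| Assumed risk at 10/15/20/25 cmH₂O | Chi-square | Isotonic | Trend |
|---|---|---|---|
| 10/17/25/33% (gradual) | 66% | 78% | 82–83% |
| 5/12/20/28% (gradual) | 77% | 87% | 91% |
| 10/20/30/40% (gradual) | 86% | 93% | 95% |
| 10/10/40/40% (step) | 99% | 100% | 99% |
| 5/5/5/25% (late step) | 87% | 91% | 85% |
| 5/30/30/30% (early step) | 92% | 95% | 79–80% |

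Respecting the order gains 7 to 17 points under gradual rises. Under steps the isotonic test gains 0 to 4 points, and the trend test can fall below the chi-square.

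**Precision of a single arm.** The Wilson 95% interval is [p + z²/2n ± z√(p(1−p)/n + z²/4n²)] / (1 + z²/n). With n = 45:

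- 0/45 has an upper limit of 3.84/48.84 = 7.9%;
- 2/45 gives 1.2 to 14.8%;
- 4/45 gives 3.5 to 20.7%.

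Even an arm without events leaves a visible risk open, so the interval belongs beside the estimate.

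**The case against.** **The planned tests are valid and the arm incidences already estimate risk.** This stands. Each arm's incidence does estimate the risk at its pressure, and the chi-square and Bonferroni pairs control error for the questions they ask. Once a risk level is fixed, simply reading the observed arm risks against it does nearly as well as an isotonic estimate. With an illustrative 15% level, the right pressure is named in about 54, 57 and 69% of trials under the three gradual rises, against 55, 58 and 69% for isotonic. Most of the benefit comes from fixing the level in advance.

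**A reader might infer that the plan would usually name too high a pressure.** The documents do not support this. They nowhere say that a pressure counts as safe if it is not significantly worse than 10 cmH₂O. An error rate for such a rule would score something the plan does not contain. The low pairwise power supports only a warning against that reading.

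**The logistic regression could carry pressure as a factor.** Nothing excludes it. But the sentence is generic and names neither pressure nor Substudy 2, so it does not commit the analysis to a pressure-response estimate.

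**A reader might infer that the primary outcome is undefined.** That goes too far. Objective 2 and the Substudy 2 title both name ultrasonography. What is missing is one sentence in the outcome definition.

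**The choice among isotonic, trend and logistic methods is preference.** Agreed. Each does better under some shapes, and the documents give no rates with which to choose. The point is to name one in advance.

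**Conclusion.** The point holds as a mismatch between objective and analysis. Substudy 2 promises a threshold, and the plan supplies an unordered test of any difference plus pairs with little power (about 5 to 13% for neighbouring pressures 10 points apart). It should be corrected, but it does not invalidate the planned tests.

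Under the assumed gradual rises, an order-respecting overall test raises power from 66, 77 and 86% to 78, 87 and 93% (isotonic) or 82–83, 91 and 95% (trend). If the risk jumps in a step, the gain is small, and under an early step the trend test loses (79–80% vs 92%). These figures rest on 45 per arm, six pairs and risks that the documents do not give. The comparison used the chi-square version of the overall test, not Fisher's. That no threshold estimate or rule is stated can be read from the text and depends on none of these assumptions.

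The unnamed diagnosis is a minor wording gap. Nothing here says which pressure is safe or what risk is acceptable.

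**What to change.** 1. **Main result.** Report the insufflation risk in each pressure arm with a 95% confidence interval (Wilson, for example). Add one pressure-risk estimate that respects the order, isotonic or logistic, named in advance. Read it against a risk level that the investigators fix and record before analysis.
2. **Overall test.** For Substudy 2, replace the unordered test with one named order-respecting test at two-sided 0.05. If isotonic, run it in both directions at one-sided 0.025 each and say so. If trend, accept the loss under an early step.
3. **Pairs.** Keep them secondary, state how many there are, and state that non-significance does not show a pressure to be safe.
4. **Outcome wording (minor).** In Substudy 2, state that the ultrasonographic diagnosis defines the primary outcome, or name the other. Report the remaining one as a sensitivity analysis.

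The cost is wording in the analysis and outcome sections and one decision by the investigators. Arms, procedures and sample size do not change. The isotonic test needs a short program, and it gives up 2 to 5 points to the trend test under the gradual rises in the table. No method will locate a threshold sharply at this size. With assumed risks of 5/10/20/35%, a logistic estimate of the pressure giving an illustrative 10% risk ran from about 9 to 18 cmH₂O (2.5th to 97.5th percentile). The report should say so.

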Substudy 3: A comparison of video intubation stylet and video laryngoscope in tracheal intubation: an open-label randomized controlled trial

Eligible patients will be randomly allocated 1:1:1, stratified by body mass index $> 50 \text{ kg}\cdot\text{m}^{-2}$, to group 1 (video intubating stylet), group 2 (video laryngoscopy), or group 3 (direct laryngoscopy). Tracheal intubation will be performed by experienced attending anesthesiologists who have performed at least 100 cases each with Trachway® video intubating stylet, GlideScope® video laryngoscopy, and Macintosh direct laryngoscopy. The anesthesiologist performing tracheal intubation is blinded to all preoperative evaluations.

In group 1, a tracheal tube (ConvaTec, Berkshire, England, UK) in appropriate sizes is preloaded over the Trachway® video intubating stylet (TVI-4050, Markstein Sichtec Medical Corp, Taichung, Taiwan), which is introduced into oral cavity to visualize the epiglottis and guided to glottis via a monitor after full neuromuscular blockade is achieved. In group 2, a tracheal tube is preloaded over a GlideRite® stylet, which is specifically designed to work with GlideScope® video laryngoscope (Verathon Medical, Bothell, WA, USA). GlideScope® blade size 3 (GS-3) or 4 (GS-4) is used in all patients. In group 3, tracheal tubes are prepared with a hockey stick-shaped stylet, and direct laryngoscopy is performed using a size-3 or -4 Macintosh blade (Rüsch Inc., Duluth, GA, USA). In all patients, backward, upward, and rightward pressure on the larynx and Sellick maneuvers are allowable to obtain the best glottic view.^{55,56} If the initial intubation attempt fails or is terminated for desaturation (defined as $\text{SpO}_2 < 92\%$) or need to change the patient's position, the intubation device will be removed, and manual bag mask ventilation will be performed. Intubation failure is defined as more than three intubation attempts or need to change intubation devices. Any intubation rescue techniques will be used at the discretion of the staff anesthesiologist.

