Primary outcome is the best glottis visualization, graded according to Cormack and Lehane's classification with external laryngeal pressure applied.⁵⁷ Glottic views graded as III or IV are regarded as difficult. Secondary outcomes are number of intubation attempts, the percentage of glottic opening (POGO) score, time to intubation, lowest SpO_2 during intubation, and ease of intubation. Each video stylet or laryngoscope blade insertion is defined as an intubation attempt. Minor adjustments of patient's position or tube stylet are not considered separate attempts. The POGO score is defined by the best glottis visualization (0%, 25%, 50%, 75%, or 100%).⁵⁸ Time to intubation is defined as the interval between intubating stylet or laryngoscope insertion into oral cavity and EtCO_2 detected. Ease of intubation is a subjective assessment of anesthesiologists, rated as (1) very easy, (2) easy, (3) moderate, (4) difficult, and (5) impossible.⁵⁹ Safety outcomes are upper airway injury (bleeding, abrasion or laceration), dental injury (bleeding, trauma, fracture), respiratory complications (laryngospasm, bronchospasm, aspiration), cough (mild, moderate, severe), sore throat (mild, moderate, severe), and hoarseness (noticed by the patient only, apparent to an observer). Research staff blinded to group allocation will evaluate the complications at the 2nd and 24th postoperative hours.

Substudy 4: An investigation of the putative benefits of goal-directed hemodynamic therapy targeting cardiac index in obese patients undergoing laparoscopic sleeve gastrectomy: an open-label randomized controlled trial

At the operation room, we will apply the Masimo Radical 7 pulse oximetry (Masimo Corp., Irvine, CA, USA) to the fingers of all enrolled patients to measure perfusion index and SpO₂ throughout the surgery. After the placement of a tracheal tube, patients will receive ventilator support with the tidal volume 6–8 ml·kg⁻¹ ideal body weight, a respiratory rate of 10–15 min⁻¹ and PEEP 5 cmH₂O applied by the ventilator.⁶⁰ The FiO₂ will be set at 0.3–0.7 to maintain SpO₂ ≥ 98% throughout the surgery. Each patient will be randomly allocated to one of each of the following two groups: goal-directed hemodynamic therapy and control.

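### Substudy 3: Bonferroni across all device pairs is valid but gives up power on the one contrast the objective names, stylet versus video laryngoscope; naming it as the primary contrast is a cheap improvement

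*Combined protocol and SAP*

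**What the plan says.** The Statistical Analysis section plans a global test first: "For three and four group comparisons, chi-square tests or Fisher's exact tests will be used for categorical variables", with one-way ANOVA or Kruskal-Wallis for continuous outcomes. It then says that post hoc "pairwise comparisons will be performed using the Bonferroni correction". The significance level is two-sided 0.05. The section does not say whether the pairwise tests depend on a significant global test, how many pairs are counted, or whether any pair has priority.

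Research Objective, item 3, names one contrast: "To compare the effectiveness and safety between video intubating stylet and video laryngoscope in the placement of tracheal tubes". The Substudy 3 title names the same one: "A comparison of video intubation stylet and video laryngoscope in tracheal intubation: an open-label randomized controlled trial". Substudy 3 nevertheless randomises three arms, the third being direct laryngoscopy: "Eligible patients will be randomly allocated 1:1:1, stratified by body mass index" above or below 50.

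The primary outcome is the best Cormack-Lehane view, with grades III and IV counted as difficult. Sample Size Estimation sets the arm size with "To allocate 60 subjects to each group of video intubating stylet, video laryngoscopy, and direct laryngoscopy in Substudy 3" and gives no event rate, effect size or power for that comparison.

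**The concern.** Bonferroni treats the three device pairs as equally important, but the objective and the title do not. If all three pairs are counted, the contrast the substudy is named after is tested at a third of the available significance level, with only 60 patients per arm and no power calculation behind that number. A real difference between stylet and video laryngoscope is then more likely to be reported as non-significant than it need be. Other procedures aim at the same 5% family-wise error for the endpoint and give this contrast more power, with no extra patients.

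**Working it through.** **The plan's own figure.** The only powered sample size is that of Substudy 4: 30% versus 55%, type I error 5%, type II error 10%, 80 per group. The two-sided pooled formula without continuity correction gives 80.1 per group, and power at 80 is 89.97%, so the figure reproduces. The 60 per arm of Substudy 3 is 180/3 and has no power basis to reproduce.

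**Inputs.** From the documents: three arms, 60 per arm, two-sided 0.05, Bonferroni. Assumed: that all three pairs are counted (0.05/3 = 0.0167), that the outcome is analysed as difficult view yes/no, and the difficult-view rates, written below as stylet/video/direct.

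**Step 1: one pair on its own.** Power = Φ{(|p₁ − p₂|√n − z√(2p̄(1 − p̄))) / √(p₁(1 − p₁) + p₂(1 − p₂))}, with z = 1.960 at 0.05 and z = 2.394 at 0.0167.

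- 5% vs 20%, n = 60: |p₁ − p₂|√n = 0.15 × 7.746 = 1.162; the two square roots are 0.468 and 0.456. At 0.05: Φ(0.54) = 0.705. At 0.0167: Φ(0.09) = 0.537.
- 10% vs 25%, n = 60: the square roots are 0.537 and 0.527. At 0.05: Φ(0.21) = 0.582. At 0.0167: Φ(−0.24) = 0.407.

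In patients, 80% power at 0.0167 rather than 0.05 needs about ((2.394 + 0.842)/(1.960 + 0.842))² = 1.33 times as many; for 10% vs 30%, 83 per arm instead of 62.

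**Step 2: why full 0.05 is allowable with three arms.** If any two of the three pairwise null hypotheses are true, all three arms are equal. The closed family is therefore the global null plus the three pairs. Once the three-group test is significant at 0.05, each pair can be tested at 0.05 with family-wise control. Separately, a contrast placed first in a fixed order may use the full 0.05 without any global test.

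**Step 3: exact enumeration** of all 61³ outcomes at 60 per arm, uncorrected chi-square tests. Power for stylet versus video laryngoscope:

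| Assumed rates | Bonferroni, no global test required | Closed testing | Tested first at 0.05 |
|---|---|---|---|
| 5/20/20% | 56.4% | 65.0% | 73.0% |
| 5/20/30% | 56.4% | 72.1% | 73.0% |
| 10/25/17% | 41.1% | 46.6% | 58.5% |
| 5/20/12% | 56.4% | 60% | 73.0% |

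The gain from closed testing depends on the third arm: 65.0 − 56.4 = 8.6 points in the first row, 15.7 in the second, and only 4 to 6 when direct laryngoscopy lies between the other two. The gain from testing the named contrast first does not depend on the third arm: 16.6 points (5% vs 20%) and 17.4 points (10% vs 25%). With pairwise Fisher tests all levels are lower but the order is the same (5/20/20%: 47.3%, 59.4%, 62.7%).

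**Step 4: family-wise error.** Over full and partial null configurations, closed testing with chi-square gave 3.8% to 5.3%; the excess over 5% comes from the large-sample approximation, and with pairwise Fisher tests it stayed at or below 5.0%. The first-place test carries the same approximation (up to 5.25%). When only one pair was truly equal, Bonferroni used 1.1% to 1.7%.

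**Step 5: four arms.** The three-arm argument does not carry over. A significant global test followed by every pair at 0.05 would give a family-wise error of 9.7% to 12.2% with four arms, so the shortcut must not be used for the pressure groups of Substudy 2.

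**The case against.** Bonferroni is a standard, pre-specified correction. It controls the error rate, biases no estimate, contradicts nothing else in the plan and comes with simple matching confidence intervals. All of that stands: this is a choice that could be better, not a mistake.

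A reader might infer that the plan corrects twice, first through the global test and then through Bonferroni. The documents do not support that. They do not say that the pairwise tests require a significant global test, and without that requirement there is only one correction.

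A reader might also infer that closed testing is free. It is not. Against Bonferroni used without a global test, the three-group test can occasionally block a rejection: at 5/20/10%, requiring it lowers Bonferroni power from 56.4% to 54.9%. Closed testing still reached 61.8% there. Matched simultaneous intervals are lost, and chi-square family-wise error can slightly pass 5%.

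Finally, every power figure rests on assumed rates and on the grade III/IV split; the plan does not say whether the four-grade scale or the split is analysed. With a smaller device difference (5/10/20%), power is 8% with Bonferroni and 15% with closed testing, inadequate either way. No choice of multiplicity rule makes up for the missing power basis of the 60 per arm.

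**Conclusion.** The point holds as a cheap improvement, not as an error in the plan. Counting all three device pairs, Bonferroni tests the contrast named in Objective 3 and the Substudy 3 title at 0.0167. Under the assumed rates in the table, testing that contrast first at 0.05 raises its power by about 17 points, and closed testing raises it by about 4 to 16. In every scenario with a true difference that was run, both had higher power for this contrast than Bonferroni; the size depends on rates the documents do not give. The 5% family-wise claim refers to one endpoint of Substudy 3, not to its secondary outcomes or to the four substudies together.

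**What to change.** For Substudy 3, replace the Bonferroni sentence with: *Stylet versus video laryngoscope is the pre-specified primary contrast and is tested first at two-sided 0.05; if it is significant, the two comparisons with direct laryngoscopy are tested with Holm at 0.05.* By the three-arm argument above, Holm is more cautious than strictly needed at that second step, but it is simple to state.

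If the investigators prefer to give no contrast priority: *If the three-group test is significant at 0.05, each pair is tested at 0.05 (closed testing, valid for three arms only).*

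For pairwise tests among the four pressure arms of Substudy 2, use Holm in place of Bonferroni; it holds the same error rate and is never less powerful.

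The cost is a few sentences, settled before outcome data are seen by arm, and no extra patients. The downsides should be accepted openly:

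- Bonferroni simultaneous intervals no longer match the tests, so ordinary 95% intervals would be shown.
- With the fixed order, the direct-laryngoscopy comparisons are exploratory whenever the first test fails. Their power cannot exceed that of the first test (73% or 58.5% above). If stylet and video laryngoscope are truly equal, they are formally tested only about 5% of the time. If those comparisons matter as much, closed testing is the better choice.
- With closed testing, the global test can occasionally block a pair, and chi-square family-wise error can reach about 5.3%.
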